7.1.2. Women of Non-childbearing Potential

To be considered sterilized or infertile, females must have undergone surgical sterilization (bilateral tubectomy, hysterectomy, or bilateral ovariectomy) or be post-menopausal (defined as at least 12 months amenorrhea without an alternative medical cause; this will be confirmed with estradiol and FSH tests).

7.1.3. Male Subjects

Male subjects with a female sexual partner of childbearing potential must commit to practice highly effective methods of contraception (e.g., condom, vasectomy) and abstain from sperm donation during the trial and for 2 weeks after the EOT visit.

Nevertheless, their partners, if they are women of childbearing potential, must agree to practice contraception and to use a highly effective method of contraception during the trial and for 4 weeks after the EOT visit. Such methods include:

- Combined (estrogen and progestogen containing) hormonal contraception associated with inhibition of ovulation (oral, intravaginal, transdermal)
- Progestogen-only hormonal contraception associated with inhibition of ovulation (oral, injectable, implantable)
- Intrauterine device
- Intrauterine hormone-releasing system

8. INVESTIGATIONAL MEDICINAL PRODUCT(S)

8.1. Dosage and Administration

All subjects will receive a single SC dose of apraglutide (5 mg). Each apraglutide treatment will be given on Day 1, within 30 minutes following a light breakfast.

8.2. Maintaining the Blind

No blinding procedures are necessary for this open-label trial.

8.3. Treatment Assignment

Once eligibility has been confirmed, the subject will be enrolled. In Part 1, subjects will be assigned to either Cohort 1 (moderate hepatic impairment) or Cohort 2 (normal hepatic function) depending on hepatic function. In Part 2, subjects will be assigned to Cohort 3 (mild hepatic impairment). All subjects will receive 5 mg apraglutide.

8.4. Packaging and Labeling

Packaging and labeling of the IMP is performed by the Clinical Trial Supply vendor in accordance with Good Manufacturing Practice and applicable regulatory requirements.

The freeze-dried apraglutide powder is filled in 2 mL vials, sealed with rubber stoppers and aluminum caps. The subject boxes and individual vials will be labeled according to Annex 13, EudraLex Volume 4 [[EudraLex, 2010](#)] and national regulatory requirements.

The CRU will be provided with enough supply for all subjects randomized in the trial. Details are included in the Pharmacy Manual.

8.5. Preparation

Reconstitution and preparation of the solution for SC administration will be performed using aseptic techniques following all applicable local guidelines. Guidelines detailing specific instructions for IMP handling will be made available in a Pharmacy Manual that will be provided to the site.

For reconstitution, sterile water will be injected into the vial to obtain a sterile solution. The vial will be gently swirled until its contents are completely dissolved and the contents of the vial verified to be free of foreign particles.

After reconstitution, the IMP must be injected within a maximum of 2 hours from completing reconstitution to ensure sterility is maintained.

The solution can be drawn up into the syringe immediately following reconstitution and kept at room temperature until administration within 2 hours of reconstitution, or the syringe can be drawn up just before administration. The required amount of reconstituted apraglutide (0.2 mL for 5 mg) will be drawn from the vial into the syringe for SC injection. After drawing up the syringe, it will be inspected for foreign particles and used if judged acceptable for administration.

8.6. Handling and Storage

The Investigator must ensure that the IMP (apraglutide) is stored between 2–8°C in a secure location with controlled access when at the site. At the site, the temperature will be monitored at least once per hour, and recorded in a temperature log as per the policies and guidelines of the site and prior to IMP dispensation. Temperature deviations outside the allowed range must be reported and evaluated prior to use of the IMP. Details will be provided to the site in a Pharmacy Manual.

Based on results from ongoing stability studies, the IMP has a shelf-life of 36 months when stored at 5±3°C. The shelf life may be extended as more data become available.

8.7. Product Accountability and Assessment of Compliance

The Investigator is responsible for maintaining records of all IMP vials and sterile water for injection ampoules received and administered to subjects (IMP accountability). The amount of unused IMP at site will be verified by a Monitor during the trial against used vials. If the Monitor's verification against used vials is restricted by site standard operating procedures, then this verification will be performed by the Monitor using site records in accordance to site-specific IMP destruction policies.

Any discrepancies between the amount of IMP (including sterile water) received and administered must be documented.

The IMP administration time and site of administration (injection) performed at the site will be documented in the subject's medical record.

Compliance will be assessed by recording the injected volume in the IMP accountability log and, unless restricted by the site standard operating procedures, will be verified by a Monitor during the trial against used vials. Compliance will also be assessed during IMP accountability.

8.8. Return and Destruction

All used IMP vials and water for injection ampoules are to be accounted for and kept at site for final reconciliation by the Monitor before being returned or destroyed at the end of the trial according to the Pharmacy Manual. If such final reconciliation by the Monitor is restricted by site standard operating procedures, then this reconciliation will be performed in accordance with site-specific IMP destruction policies. Details are described in the Pharmacy Manual.

8.9. Treatment of Investigational Medicinal Product Overdose

Apraglutide will be administered as a single SC injection by trained trial staff. An overdose is not anticipated. Apraglutide has been tested in humans in a range between 2.5 mg and 56.9 mg. No maximum tolerated dose has been established. If overdose is suspected, the Investigator must treat the subject as appropriate and inform the Sponsor according to specified guidelines ([Section 11.3](#)).

8.10. Occupational Safety

No specific risks have been identified for staff handling the IMP. However, standard precautions should be taken to avoid needle stick injuries. The Material Safety Data Sheets will be provided to the Investigator where required by local regulations or is available upon request from the Sponsor.

9. NON-INVESTIGATIONAL MEDICINAL PRODUCTS

Not applicable.

This document is proprietary to VectivBio and for restricted circulation and access only.

10. CONCOMITANT MEDICATIONS AND NON-DRUG THERAPIES

Any prior or concomitant treatments will be reported in the CRF along with their daily dosage, duration, and reasons for administration. Concomitant drug and non-drug treatment will be collected. All subjects will be questioned about concomitant treatment at each clinic visit. Treatments taken within 28 days of the first period of treatment will be documented as prior treatment.

Subjects who have received any concomitant treatment may be withdrawn from the trial at the discretion of the Investigator.

10.1. Permitted Medications

No new medication should be started during the trial, unless medically necessary and prescribed by the Investigator or another qualified designee involved in the subject's care and being aware of the subject's participation in the trial.

10.2. Prohibited Medications

- Growth hormone, glutamine or growth factors such as GLP-1, GLP-2 or analogs within the last 3 months prior to Screening and throughout the trial
- Systemic corticosteroids, methotrexate, cyclosporine, tacrolimus, sirolimus, infliximab, or other biologic therapy/immune modifiers within 30 days of Screening and throughout the trial. A dose of up to 1-2 g/kg/day of methylprednisolone or equivalent corticosteroid is allowed
- Citrulline supplements, mycophenolate mofetil, and Janus kinase inhibitors are not allowed during the trial
- Use of prescription drugs within 14 days or five half-lives or non-prescription drugs and dietary and herbal supplements within 7 days or five half-lives, if known, (whichever is longer) prior to IMP dosing unless deemed necessary by the Investigator for the treatment of concurrent disease

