4.3. Stopping Rules

4.3.1. Trial Stopping Rules

The trial can be stopped after completion of Part 1 according to the criterion described in [Section 4.1.1](#).

If the Investigator, the Sponsor, or the Safety Medical Monitor (who reviews medical information and safety data, and consults with the site on eligibility criteria) becomes aware of conditions or events that suggest a possible hazard to subjects if the trial continues, the trial may be terminated after appropriate consultation between the relevant parties. The trial may also be terminated early at the Sponsor's discretion in the absence of such a finding.

Conditions that may warrant termination include, but are not limited to:

- The discovery of an unexpected, significant or unacceptable risk to the subjects enrolled in the trial
- Failure of the site to enroll subjects at an acceptable rate
- Enrollment and further dosing of new subjects will be interrupted if two or more subjects experience AESIs such as fluid overload, persistent abdominal pain, gall bladder, biliary and pancreatic disease of Grade 3 and above, according to the National Cancer Institute – Common Terminology Criteria for Adverse Events (NCI-CTCAE), version 5 [\[CTCAE, 2017\]](#) of moderate intensity and/or if one or more subjects experience a Grade 4 event (unless clearly not attributable to the trial drug)

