5.3. Eligibility Criteria

5.3.1. Inclusion Criteria

All Subjects

1. Signed and dated ICF prior to any trial-mandated procedure
2. Male or female subjects aged from 18 to 75 years at the time of signing the ICF
3. Body mass index range from 18 to 35 kg/m² and a body weight more than 50 kg
4. Women of childbearing potential must agree to practice effective contraception and to use a highly effective method of contraception (see [Section 7.1.1](#)) during the trial and for 4 weeks after the EOT visit
5. Postmenopausal women. Postmenopausal status is defined as no regular menstrual bleeding for at least 12 months prior to inclusion. Menopause will be confirmed by a serum estradiol concentration of <20 pg/mL and a serum follicle-stimulating hormone (FSH) level of >40 IU/L

6. Male subjects with a female partner of childbearing potential must commit to practice highly effective methods of contraception (e.g., condom, vasectomy) and abstain from sperm donation during the trial and for 2 weeks after the EOT visit. Their partners, if they are women of childbearing potential, must agree to practice effective contraception and to use a highly effective method of contraception during the trial and for 4 weeks after the EOT visit. See [Section 7.1.3](#)
7. Able to participate, willing to give written informed consent, and comply with the trial restrictions
8. Negative result of SARS-CoV-2 polymerase chain reaction testing in the morning prior to admission to the CRU (Day -1)

Additional Inclusion Criteria for Subjects with Normal Hepatic Function (Cohort 2)

9. No clinically relevant abnormalities identified by a detailed medical history, full physical examination, measurement of heart rate, 12-lead ECG, and clinical laboratory tests

Additional Inclusion Criteria for Subjects with Impaired Hepatic Function (Cohorts 1 and 3)

10. Diagnosis of cirrhosis (due to parenchymal liver disease), which is confirmed and documented by medical history and at least one of the following: physical examination, hepatic ultrasound, computed axial tomography scan, magnetic resonance imaging, and/or liver biopsy
11. Cohort 1: moderate liver disease (Child-Pugh B) which has been clinically stable (defined as no clinically significant change in disease status) for at least 1 month prior to screening at the discretion of the Investigator

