5.3.2. Exclusion Criteria

All Subjects

1. History of clinically significant GI, bronchopulmonary, neurological, cardiovascular, endocrine, or allergic disease
2. Known hypersensitivity to the IMP, any of their excipients or drugs of the same class
3. If capable of reproduction, unwilling to use an effective form of contraception
4. If female of child-bearing potential, a positive urine/blood pregnancy test
5. Breast-feeding women
6. Positive urine/blood test for alcohol and drugs of abuse at Screening and on Day - 1

7. Use of prohibited medications or herbal remedies as detailed in [Section 10.2](#)
8. Known presence or history of intestinal polyps
9. Known presence or history of any type of cancer
10. Pancreatic events such as acute pancreatitis, pancreatic duct stenosis, pancreas infection, and increased blood amylase and lipase ($>2.0\text{--}5.0 \times$ upper limit of normal range)
11. Participation in an investigational drug or device study within 30 days prior to Screening
12. Donation of blood over 500 mL within 2 months prior to Screening
13. Heavy use of tobacco products (i.e., smokes more than 10 cigarettes per day)
14. Concomitant disease or condition that could interfere with, or for which the treatment of might interfere with, the conduct of the study, or that would, in the opinion of the Investigator, pose an unacceptable risk to the subject in this trial
15. Any intercurrent clinically significant illness in the previous 28 days before Day 1 of this study as determined by Investigator
16. Positive results to human immunodeficiency virus (HIV) antigen/antibody combo, hepatitis A (HAV), hepatitis B surface antigen (HBsAgB), or hepatitis C virus (HCV) tests. Subjects recovered from hepatitis B or C can be enrolled, i.e., they have markers of the infection, but the viral load is undetectable. Subjects with evidence of an acute or chronically active hepatitis B or C infection will be excluded. A subject being anti-HBs positive, with an undetectable viral load and with history of vaccination against hepatitis B are eligible for enrolment
17. Unwillingness or inability to comply with the study protocol for any other reason

Additional Exclusion Criteria for Subjects with Normal Hepatic Function (Cohort 2)

18. Any clinically relevant abnormal laboratory test results that are not in line with subject with normal hepatic function status at the discretion of the Investigator

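### Protocol 10.2 allows corticosteroids up to a two-fold range, so it fixes no single ceiling, and the printed unit needs checking against the source

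*Protocol*

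**What the plan says.** The second bullet of Protocol Section 10.2 lists the immunosuppressive drugs that are not allowed: "Systemic corticosteroids, methotrexate, cyclosporine, tacrolimus, sirolimus, infliximab, or other biologic therapy/immune modifiers within 30 days of Screening and throughout the trial". The same bullet then makes an exception for one class: "A dose of up to 1-2 g/kg/day of methylprednisolone or equivalent corticosteroid is allowed".

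Section 10.2 is also an eligibility rule. Exclusion criterion 7 in Section 5.3.2, repeated in the Synopsis, excludes a subject for "Use of prohibited medications or herbal remedies as detailed in" Section 10.2. Because the limit is per kilogram, body weight matters. Inclusion criterion 3 in Section 5.3.1 requires "Body mass index range from 18 to 35 kg/m² and a body weight more than 50 kg".

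Other provisions bear on the same medication:

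- Section 10: "Any prior or concomitant treatments will be reported in the CRF along with their daily dosage, duration, and reasons for administration". It also states: "Subjects who have received any concomitant treatment may be withdrawn from the trial at the discretion of the Investigator".
- Section 10.1: "No new medication should be started during the trial, unless medically necessary and prescribed by the Investigator or another qualified designee".
- The fourth bullet of Section 10.2 sets a general pre-dose washout for prescription drugs, which the Investigator may waive to treat concurrent disease.
- Section 4.3.1 gives a role to a "Safety Medical Monitor (who reviews medical information and safety data, and consults with the site on eligibility criteria").
- Exclusion criteria 14 and 15 let the Investigator exclude subjects for interfering conditions or treatments, and for recent significant illness.

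None of these states a corticosteroid dose.

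**The concern.** A ban with a dose-limited exception works only if the limit is one number in a known unit. Here the limit is a range, and its two ends differ two-fold. Site staff who follow the text faithfully could classify the same subject differently, some taking the lower value as the ceiling and some the higher.

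The unit raises a separate question. It appears once, nothing elsewhere confirms it, and multiplied by the minimum body weight it gives tens of grams per day or more. That is reason enough to compare it with the source document.

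What is at stake is consistent application of an eligibility and concomitant-medication rule. It also affects whether a case is entered as an eligibility non-compliance (SAP Section 13.3) or a protocol deviation (SAP Section 12.0).

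**Working it through.** The documents do not derive the limit from anything, so there is no calculation of the plan's to reproduce. The check is a reading of the text plus simple arithmetic.

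**Inputs**

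- Values in the exception: 1 and 2, per kg per day (Protocol 10.2).
- Unit as printed: g (Protocol 10.2, one occurrence).
- Body weight: more than 50 kg (Protocol 5.3.1, criterion 3).
- Weights of 70 and 100 kg: assumptions, for illustration only.

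**Step 1: the two ceilings, in any unit.** Ratio = higher value / lower value = 2 / 1 = 2.0. The ratio does not depend on unit or weight, so confirming or correcting the unit alone would still leave two ceilings.

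**Step 2: doses whose status is undetermined under this bullet.**

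| Dose (units/kg/day) | Ceiling read as 1 | Ceiling read as 2 |
|---|---|---|
| up to 1 | within the exception | within the exception |
| above 1, up to 2 | breaches the bullet | within the exception |
| above 2 | breaches the bullet | breaches the bullet |

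The width of the middle band is (2 − 1) × weight. With weight above 50 kg it is more than 50 units/day for every eligible subject. This describes the wording; it does not estimate how many subjects fall there.

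**Step 3: daily amounts, only if the printed unit is correct.** Ceiling = value × weight.

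| Weight | Lower value | Higher value |
|---|---|---|
| 50 kg (eligible subjects weigh more) | 1 × 50 = 50 g/day | 2 × 50 = 100 g/day |
| 70 kg (assumed) | 1 × 70 = 70 g/day | 2 × 70 = 140 g/day |
| 100 kg (assumed) | 1 × 100 = 100 g/day | 2 × 100 = 200 g/day |

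So every eligible subject's ceiling would exceed 50 g/day on the lower value and 100 g/day on the higher.

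**Step 4: does anything else settle it?** No other section of the protocol or SAP gives a corticosteroid dose, a single ceiling or a different unit. Nothing resolves the range or confirms the unit.

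**Step 5: is this bullet decisive alone?** No. The bullets of Section 10.2 are cumulative. A prescription corticosteroid taken in the pre-dose window must also satisfy the fourth bullet, and one started during the trial must satisfy Section 10.1. Falling within the exception is necessary for permission but does not complete it.

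**The case against.** The strongest reply is that this is a small wording matter. A reader may sensibly take the higher value as the maximum. Dosage, duration and reason are recorded. The Safety Medical Monitor consults on eligibility. The Investigator can withdraw a subject or apply exclusion criteria 14 and 15, and Cohort 2 is restricted further by inclusion criterion 9 and exclusion criterion 18. The trial gives a single dose to about 16 to 32 subjects (Protocol Section 5.2), and the documents do not show that anyone is likely to use the exception.

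Most of this stands, and it sets the weight of the point. It does not remove the point. The text does not say that the higher value governs, and that reading leaves the lower value with no function. The safeguards record a dose or give someone discretion; none supplies the ceiling to be applied.

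Four stronger readings are tempting, and the documents do not support them:

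- *The ban and the exception contradict each other.* They do not. A ban followed by a dose-limited exception is coherent; the fault lies in how the limit is stated.
- *The sponsor wrote the wrong unit, and the exception therefore empties the ban.* The unit is printed once in text read from PDF, so a reading error cannot be excluded. The drug name is spelled two ways in the same sentence about Child-Pugh C (Synopsis, Trial Design, and Section 1.2.2), and the text cannot show whether the source or the reading is responsible. Whether the ban would lose its effect depends on the doses subjects take, which the documents do not give.
- *A subject between the two values is permitted on the lenient reading.* Such a subject meets only this bullet; the other rules still apply.
- *The PK comparison is at risk.* Nothing in the documents links this exception to the PK endpoints.

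**Conclusion.** The point holds as a minor defect. The exception in Protocol 10.2 gives two upper values in the ratio 2.0, so it fixes no single ceiling in any unit, and nothing else in the protocol or SAP resolves it. Because exclusion criterion 7 refers to Section 10.2, the unclear threshold is part of an operative eligibility rule as well as the rule on medication during the trial.

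This conclusion rests only on the two printed values. The gram-per-day figures rest also on the printed unit; if the source shows another unit, those figures fall and the two-ceiling defect remains. Practical impact is low given the safeguards, and no effect on endpoints, analyses or sample size is claimed.

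**What to change.** The sponsor should check the unit in Section 10.2 against the source document and reconcile the sentence so that it states one unambiguous limit in one confirmed unit. The value is for its clinical team to decide, and none is proposed here. Exclusion criterion 7 follows by cross-reference and needs no edit of its own.

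The cost is a one-line protocol correction, with no change to the SAP.

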11. ADVERSE EVENTS AND SERIOUS ADVERSE EVENTS

11.1. Adverse Events

An AE is any untoward medical occurrence in a patient or clinical investigation subject administered a pharmaceutical product that does not necessarily have a causal relationship with this treatment. An AE can therefore be any unfavorable and unintended sign (including an abnormal laboratory finding), symptom, or disease temporally associated with the use of a medicinal (investigational) product, whether or not related to the medicinal (investigational) product.

Adverse events will be collected for all subjects from when the ICF is signed until the EOT visit.

11.1.1. Intensity of Adverse Events

The intensity of AEs is graded using the NCI-CTCAE scale ([CTCAE, 2017](#)).

Where the event is not specified in the scale, then the following definitions should be used to determine mild, moderate and severe events:

- Grade 1 (Mild): the event may be noticeable to the subject. It does not usually influence daily activities, and normally does not require intervention
- Grade 2 (Moderate): the event may make the subject uncomfortable. Performance of daily activities may be influenced, and intervention may be needed
- Grade 3 (Severe): the event may cause noticeable discomfort and usually interferes with daily activities. The subject may not be able to continue in the trial, and treatment or intervention is usually needed
- Grade 4 (Life-threatening): the subject was at risk of death; this does not apply if the subject might have been at risk of death if the event was more severe
- Grade 5 (Fatal)

A mild, moderate, or severe (Grades 1–3) AE may or may not be serious. Life-threatening and fatal (Grades 4 and 5) are always serious. These terms are used to describe the intensity of a specific event. Medical judgment will be used on a case-by-case basis.

